2.1.1.2 Study periods

The following study periods will be considered for analysis:

- Screening period (SCR): from the date of signing informed consent form (ICF) to, and not include the date of the first ligelizumab treatment (i.e. V201) in extension, or the first visit in the first observation period (i.e. V101), whichever comes first.
- First observation period (OBS1): from Visit 101 up to Visit 199. The duration of OBS1 period for each subject varies, as it depends on occurrence of relapse ($UAS7 \geq 16$). Maximum duration of OBS1 is 36 weeks.
- First 12 weeks of the first half of the treatment period (TRT1A): from Visit 201 to Visit 204.
- Week 12 to Week 52 of the first half of the treatment period (TRT1B): from Visit 204 to Visit 214 or 301, whichever comes first.
- Entire first half treatment period (TRT1): from Visit 201 to Visit 214 or 301, whichever comes first.
- Second observation period (OBS2): from Visit 301 up to Visit 399. The duration of OBS2 period for each subject varies, as it depends on occurrence of relapse ($UAS7 \geq 16$). Maximum duration of OBS2 is 52 weeks.
- Second half of the treatment period (TRT2): Visit 214 to Visit 9998 (excluding Visit 301 to Visit 399)
- Follow-up period:
 - Subjects who do not complete a continuous 104-week treatment will enter the follow-up period (FU12) for 12 weeks duration and will only perform Visit 9999.
 - Subjects who have completed the full 104-week treatment period without interruption will enter the follow-up period (FU52) of 52 weeks duration and will perform Visit 501 to Visit 9999 (Week 116 to Week 156).

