2.1.1.3 Study Day and Study Week

2.1.1.3.1 Study Day

Study day is defined with respect to extension and will be used for all efficacy and safety analyses. The first day of administration of study treatment (first dose) of extension study is defined as Day 1.

All other study days will be labeled relative to Day 1. For event dates on or after Day 1, study day for a particular event date will be calculated as [Date of event] - [Date of first dose] + 1. For the dates before Day 1, study day for an event date will be calculated as [Date of event] - [Date of first dose]. Hence, study days for the following critical dates are defined as follows:

- Signing ICF (Day *a*) : [Date of signing ICF] - [Date of first dose]
- Start of OBS1 (Day *b*): [Date of Visit 101] - [Date of first dose]
- Start of TRT1 (Day 1): defined as Day 1
- Start of TRT2 (Day *c*): [Date of Visit 214] - [Date of first dose] +1
- Start of OBS2 (Day *d*): [Date of Visit 301] - [Date of first dose] +1
- Start of 52-week FU (Day *e*): [Date of Visit 501] - [Date of first dose] +1

Duration of an event will be calculated as (Event end date - Event start date + 1).

The descriptor “Day 0” will not be used.

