2.2.2 Subpopulations

The following subpopulations are defined for primary and key secondary efficacy analyses:

- **Ligelizumab retreatment subpopulation** (applicable to subjects whose preceding studies are C2302 and C2303): subjects who are treated with same dosage of ligelizumab in the two core studies (C2302 and C2303) and the extension study.
- **Ligelizumab responder retreatment subpopulation** (applicable to subjects whose preceding studies are C2302 and C2303): subjects who were treated by the same dosage of ligelizumab in the two core studies (C2302 and C2303) and the extension study and achieved UAS ≤ 6 at core study week 12.

Subjects who switched from placebo to ligelizumab in core studies are not included in ligelizumab retreatment subpopulation or ligelizumab responder retreatment subpopulation.

The following subpopulations are defined for relevant secondary [REDACTED]

- **PFS subpopulation** (applicable to all SAF subjects, irrespective of preceding studies): subjects who have at least one dose of ligelizumab 120 mg q4w PFS

- **Outside-of-clinic self-administration subpopulation** (applicable to SAF subjects, irrespective of preceding studies): subjects who receive ligelizumab via self-administration outside-of-clinic at least once.
- **Monotherapy subpopulation** (applicable to SAF subjects, irrespective of preceding studies): subjects who are qualified for ligelizumab monotherapy (i.e. discontinued H1-AH background medication) per investigators' decision at week 64.
- **Continuous long term treatment subpopulation** (applicable to SAF subjects, irrespective of preceding studies): subjects with an uninterrupted treatment period of 104 weeks.
- **Long term treatment subpopulation** (irrespective of preceding studies): subjects who receive ligelizumab treatment in the second half of treatment period without entering the second observation period.
- **Long term treatment with a rest subpopulation** (irrespective of preceding studies): subjects who received one-year ligelizumab treatment and move to the second observation period before moving to the second half of the treatment period.

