2.8.1.3 AE summaries for Secondary Safety Endpoints

For safety and tolerability of ligelizumab for all subjects during the study, summaries will be provided by study period. For TRT1A and TRT1B, summaries of TEAE, treatment emergent SAE (TESAE), treatment emergent AESI (TEAESI), TEAEs leading to discontinuation, TEAEs leading to death, and TEAE by severity will be provided for SAF.

For the long term treatment subpopulation, TEAE, TESAE, TEAESI, and TEAEs leading to discontinuation will be summarized for TRT1A, TRT1B, TRT2 and TRT1+TRT2.

For the long term treatment with a rest subpopulation, TEAE, TESAE, TEAEs leading to discontinuation, AESI of CCV and malignancy will be summarized for TRT1A, TRT1B, and TRT2.

In addition, a summary table of TEAE during entire treatment period was planned to be provided for the continuous long term treatment subpopulation. However, this analysis will not be conducted in the final analysis due to study early termination due to study early termination.

To investigate the safety and tolerability of ligelizumab 120 mg PFS, summaries of TEAEs, TESAEs, and TEAESIs will be provided to include the AEs after the first dose of PFS use. Only the subjects who receive at least one dose of ligelizumab 120 mg PFS use will be included in this analysis.

To investigate the safety and tolerability of ligelizumab 120 mg in all subjects who will be self-administered, summaries on TEAEs, TESAEs, and TEAESIs will be provided to include the information after the first dose using “out of clinic” self-administration. Subjects who move from self-administration back to in-clinic administration during the study, will be included in this analysis if majority (>50%) of drug use is based on “out of clinic” self-administration.

The safety and tolerability of ligelizumab 120 mg self-administration with PFS has been evaluated at the interim analysis. Those analyses will not be re-conducted in the final analysis.

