2.14.1 Final analysis sets

The enrolled set (ENR), the full analysis set (FAS), and the safety analysis set (SAF) as defined in Section 2.2, will be used for this final analysis. The following subpopulations will be considered in the safety and efficacy analyses for this final analysis:

- **Ligelizumab retreatment subpopulation** (as defined in Section 2.2.2): subjects in SAF who are treated with same dosage of ligelizumab in the extension study as in the core studies (C2302 and C2303).
- **Ligelizumab responder retreatment subpopulation** (as defined in Section 2.2.2): subjects in SAF who are treated with same dosage of ligelizumab in the extension study as in the core studies (C2302 and C2303) and achieved $UAS7 \leq 6$ at week 12 in the core studies.

- **Long term treatment subpopulation** (as defined in Section 2.2.2): subjects in SAF who receive ligelizumab treatment in the second half of treatment period without entering the second observation period. Due to study early termination, the definition of “continuous long term treatment subpopulation” will not be used for the final analysis.
- **Long term treatment with a rest subpopulation** (as defined in Section 2.2.2): subjects in SAF who received one-year ligelizumab treatment and moved to the second observation period before moving to the second half of the treatment period.
- **Self-administration subpopulation** (as defined in Section 2.13.2.1): subjects who have at least one injection with PFS administered by the participant herself/himself or a caregiver either in clinic or outside of clinic.

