
Analysis: Safety
 
Population: SAF
 
Period: TRT1A; TRT1B
	
 • TEAE, TESAE, TEAESI (crude incidence and EAIR) • TEAEs leading to discontinuation, death, (crude incidence and EAIR) • TEAE by severity (crude incidence) • Summary of vital signs, by visit • Summary of lab assessments, by visit

Entire treatment period (TRT1 + TRT2)
	

Analysis: Safety
 
Population:
 
1) Long term treatment subpopulation
 
Period: TRT1A; TRT1B; TRT2; TRT1+TRT2
	
 • TEAE, TESAE (crude incidence and EAIR), TEAESI (crude incidence and EAIR) • TEAEs leading to discontinuation (crude incidence and EAIR) • Summary of clinical notable lab abnormality (only TRT1+TRT2) • Summary of newly occurring or worsening vital signs (hypertension, hypotension, bradycardia, tachycardia; only TRT1+TRT2)

Analysis: Safety
 
Population:
 
1) Long term treatment with a rest subpopulation
 
Period: TRT1A; TRT1B; TRT2
	
 • TEAE, TESAE (crude incidence and EAIR) • TEAEs leading to discontinuation (crude incidence and EAIR) • AESI of CCV and malignancy (crude incidence and EAIR; only TRT1+OBS2+TRT2+FU) • Summary of clinical notable lab abnormality (only TRT1+OBS2+TRT2+FU)

	
 Summary of newly occurring or worsening vital signs (hypertension, hypotension, bradycardia, tachycardia; only TRT1+OBS2+TRT2+FU)
Entire study period (for the legal requirements of ClinicalTrials.gov and EudraCT)	
Analysis: Safety Population: SAF Period: Entire study	
 TEAE which are not serious adverse events with an incidence greater than 5% TESAE and SAE suspected to be related to study treatment

3 Sample size calculation

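### In the long term treatment subpopulation, TEAEs leading to discontinuation are near zero in year 1 by construction, and their pooled two-year EAIR is diluted to about 0.20 to 0.50 of the TRT2 rate

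*SAP*

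**What the plan says.** SAP 2.2.2 defines the long term treatment subpopulation as "subjects who receive ligelizumab treatment in the second half of treatment period without entering the second observation period". SAP 2.14.1 keeps this definition for the final analysis, within the Safety Set, and drops the continuous 104-week group because of early termination.

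SAP 2.8.1.3 sets the outputs: "For the long term treatment subpopulation, TEAE, TESAE, TEAESI, and TEAEs leading to discontinuation will be summarized for TRT1A, TRT1B, TRT2 and TRT1+TRT2". Table 2-16, the scope of the final analysis, gives the same periods ("TRT1A; TRT1B; TRT2; TRT1+TRT2"), and both it and Table 2-10 ask for crude incidence and EAIR of TEAEs leading to discontinuation.

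The clock starts at the first extension dose: "Start of TRT1 (Day 1): defined as Day 1" (SAP 2.1.1.3.1). SAP 2.1.1.2 sets the first period: "Entire first half treatment period (TRT1): from Visit 201 to Visit 214 or 301, whichever comes first". TRT2 runs from Visit 214 to Visit 9998. Under SAP 2.8.1.2, a subject without the event contributes all follow-up time to the EAIR denominator. The protocol glossary defines study drug discontinuation as a permanent stop. SAP 2.8.1.1 assigns TEAEs to a period by onset or worsening.

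The long term treatment with a rest subpopulation (one year on drug, then OBS2, then TRT2) has the same discontinuation row for TRT1A, TRT1B and TRT2, with no pooled discontinuation rate.

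**The concern.** Membership is settled at Week 52 or later, but person-time and events are counted from Day 1. For an event that ends treatment, year 1 is immortal time: every member is known to have passed through it without stopping.

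Two figures are affected. The TRT1A and TRT1B discontinuation cells will be near zero and will look like good first-year tolerability. The pooled TRT1+TRT2 EAIR will have a full year of denominator with almost no numerator. Read from left to right, the TRT1A, TRT1B and TRT2 columns will show discontinuation rising in year 2, and the definition alone can produce that rise. Table 2-10 places this subpopulation under the objective of safety in all subjects, which a rate conditional on reaching year 2 does not answer. The plan specifies no landmark, delayed entry or caveat.

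**Working it through.** **Period lengths.** Table 2-1 puts Week x at days 7(x−1)+1 to 7x, so Week 52 is days 358 to 364. Table 2-2a puts Week x at days 7(x−52)+358 to 7(x−51)+357, so Week 104 is days 722 to 728. Both agree with the tables as printed. A member with full exposure has 364/728 = 50% of follow-up before membership is settled.

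**Dilution.** Let N be the number of members, D1 and D2 their TEAEs leading to discontinuation counted in TRT1 and TRT2, and T mean weeks in TRT2.

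- EAIR(TRT2) = D2 / (N × T/52) per year
- EAIR(TRT1+TRT2) = (D1 + D2) / (N × (52+T)/52) per year
- With D1 ≈ 0, the ratio of pooled to TRT2 is T/(52+T)

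The documents give neither T nor a discontinuation rate. T is assumed to be 13 to 52 weeks; the termination reported in SAP section 1 makes values below 52 plausible. A constant hazard of 2, 5 or 10 per 100 patient-years (PY) is also assumed. A simulation of 2,000,000 subjects, keeping those still on treatment after 52 weeks, checks the formula.

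| Weeks in TRT2 | T/(52+T) | Pooled EAIR per 100 PY if the true rate is 2 / 5 / 10 |
|---|---|---|
| 52 | 52/104 = 0.50 | 1.00 / 2.48 / 4.87 |
| 26 | 26/78 = 0.33 | 0.66 / 1.65 / 3.28 |
| 13 | 13/65 = 0.20 | 0.40 / 1.00 / 1.98 |

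The simulated rates fall slightly below the simple product because subjects who stop contribute less than the full TRT2 length. The ratio barely depends on the hazard. With person-time from Week 52, the TRT2 rate recovers about 2, 5 and 10. Simulated year-1 discontinuations among members were 0. At 5 per 100 PY and 52 weeks of TRT2, crude two-year incidence was 4.89% in members against 9.53% in an unselected cohort.

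**Other adverse events.** Members can have these in year 1, so the distortion depends on q, the share of such events that stop treatment. With assumed event rates of 5 and 50 per 100 PY and 52 weeks of TRT2:

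| q | Year-1 rate / true rate | Two-year rate / true rate |
|---|---|---|
| 0 | 1.00 | 1.00 |
| 0.10 | 0.89 to 0.91 | 0.94 to 0.95 |
| 0.50 | 0.50 | 0.70 to 0.75 |

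This leaves out selection at Week 52 itself. Under Protocol 3.3, subjects with UAS7 ≤ 6 go to OBS2. Under Protocol 4.2, the risk-benefit review for UAS7 ≥ 16 may consider earlier adverse events. The documents give no basis for sizing either effect.

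**The case against.** A reader might infer that every adverse-event rate in this subpopulation contains guaranteed event-free time, or that serious-event risk is understated two- to five-fold. The documents do not support this. TEAEs, TESAEs and TEAESIs can occur in year 1 without ending treatment, so those rows carry only survivor selection, which is modest if few events stop treatment.

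A reader might also infer that this subpopulation supplies the only adverse-event figure spanning both treatment years. That fails too. SAP 2.8.1.3 keeps a summary after first PFS use, which Table 2-10 sets over TRT1B+TRT2 with exposure adjustment, although Table 2-16 omits it. SAP 2.8.2 and Table 2-16 add entire-study Safety Set tables for registry reporting, outside the CSR.

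Year-1 discontinuations are also not hidden. SAP 2.3.4 tabulates disposition with reasons on the FAS for TRT1A, TRT1B and TRT2. The Safety Set has TEAEs leading to discontinuation in TRT1A and TRT1B, and Table 2-10 has crude incidence by study period. The undiluted TRT2 column stands beside the pooled one, and all of this is descriptive.

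These points narrow the concern but do not remove it. In the final-analysis scope, no Safety Set EAIR of TEAEs leading to discontinuation covers TRT1+TRT2. The figure that does cover it is the diluted one. The onset rule also means year-1 cells need not be exactly zero, and any such events would raise the pooled rate above T/(52+T). The documents give no figure for how often this happens.

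Limiting every summary of these subpopulations to TRT2 would go too far: Protocol 12.5.2 calls for safety summaries of subjects with two continuous years and of those with an interruption.

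**Conclusion.** The point holds for one row. In the long term treatment subpopulation, TEAEs leading to discontinuation are near zero in TRT1A and TRT1B by construction, and the TRT1+TRT2 EAIR is about 0.20 to 0.50 of the TRT2 rate. The near-zero cells follow from the definitions alone. The size rests on D1 being close to zero and on the assumed 13 to 52 weeks of mean TRT2 exposure. The rest subpopulation shares the TRT1A and TRT1B defect but not the pooled one. Other adverse-event summaries are conditional on reaching year 2 and need a note to that effect. The change should be made: it removes a biased tolerability figure, though no test or formal comparison depends on it.

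**What to change.** Amend SAP 2.8.1.3, Table 2-10 and Table 2-16:

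- For both long-term subpopulations, report TEAEs leading to discontinuation in TRT2 only, with person-time from Visit 214.
- Add crude incidence and EAIR of TEAEs leading to discontinuation on the whole Safety Set for TRT1+TRT2, with OBS2 time excluded.
- Keep the other TEAE summaries for these subpopulations, with a note that they are conditional on reaching year 2.

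Two nearby inconsistencies can be settled in the same edit. SAP 2.8.2.1.1 assigns the TRT1+TRT2 TEAESI summary to the rest subpopulation, while 2.8.1.3 and Table 2-16 assign it to the long term treatment subpopulation. SAP 2.8.1.2 does not list discontinuation TEAEs among the EAIR types, while both tables request them.

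The cost is SAP wording, one more Safety Set table and a stated rule for OBS2. That rule must cover both the person-time gap and events that fall in OBS2 but within the 16-week treatment-emergent window after the last year-1 dose.

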2.8.2 Others

For the legal requirements of ClinicalTrials.gov and EudraCT, two required tables “Treatment emergent adverse events which are not serious adverse events with an incidence greater than 5%” and “Treatment emergent serious adverse events and SAE suspected to be related to study treatment” will be provided by system organ class and preferred term on the safety set population. These tables will not be included in the CSR.

2.8.2.1 Adverse events of special interest / grouping of AEs

2.8.2.1.1 Adverse Events of Special Interest

AESI for Ligelizumab treatment is specified as compound-level risk factors defined in the Case Retrieval Strategy (eCRS).

In the final analysis, TEAESI will be summarized for SAF for TRT1A and TRT1B, by treatment group and study period; TEAESI will be summarized for the long term treatment subpopulation for TRT1A, TRT1B, and TRT2, by treatment group and study period; TEAESI will be summarized for the long term treatment with a rest subpopulation for TRT1A, TRT1B, TRT2, and TRT1+TRT2, by treatment group and study period. AESI of CCV and malignancy will be summarized for the long term with a rest subpopulation for TRT1+OBS2+TRT2+FU.

2.8.2.1.2 Adjudicated AEs

In addition to the AESI listed above, the following AEs will be adjudicated by the independent committee. The positively adjudicated events will be listed with treatment emergent flag applied.

- Anaphylactic events
- Major cardio-cerebrovascular events
- Neoplastic events

2.8.3 Deaths

No separate listing or table will be provided from the database. Death will be reported as part of SAE with a fatal outcome.

2.8.4 Laboratory data

The summary of laboratory evaluations will be presented for 2 groups of laboratory tests (hematology and serum chemistry). Descriptive summary statistics for the change from baseline to each study visit will be presented. These descriptive summaries will be presented by laboratory test and treatment group. Change from baseline will only be summarized for subjects with both baseline and post baseline values. For categorical parameters, frequencies by categories at each visit will be summarized.

Shift tables using the low/normal/high/ (low and high) classification will be used to compare baseline to the worst on-treatment value in the first half of the treatment period separately.

The laboratory values below Lower Level of Quantification (LLQ) or above Upper Level of Quantification (ULQ) will be imputed as LLQ or ULQ in the summary tables, respectively. The numerical part of the reported result will be treated as the actual LLQ or ULQ. These laboratory values will be displayed in listings using the standard unit with the reported sign (“<” or “>”).

The number of patients with newly occurring or worsening abnormalities during the study will be listed by treatment and by study periods (as defined in section 2.1.1.2), based on the notable criteria specified in the Appendix 1 to 3 of the study protocol (See section 16.1 to 16.3 of the study protocol). A case is considered as a newly occurring abnormality if the value is not notable or missing at baseline but is notable thereafter during the study. A case is considered as a worsening abnormality if the value is notable at baseline and at least one post-baseline value during the study is worse than baseline.

If an adolescent subject turned to be an adult subject during the study, the normal range, notable criteria for analysis will be based on the age by the visit assessment.

To evaluate potential drug-induced liver injury, newly occurring liver enzyme abnormalities at any time post-baseline will also be summarized according to protocol Appendix 2.

Data from local laboratories will not be used in any of the summary analyses included in this session.

2.8.5 Other safety data

2.8.5.1 ECG and cardiac imaging data

All ECG data will be listed by treatment group, subject and visit/time, and by study period identified in Section 2.1.1.2. Newly occurring or worsening abnormalities will be flagged.

A listing of all notable abnormalities will be provided, as well as a by-subject listing of all quantitative ECG parameters.

[figure not shown]
For ECGs a notable QTc value is defined as a QTcF interval of greater than 450 ms for males or greater than 460 ms for females – all such ECGs will be flagged by the Central CRO’s cardiologist and require assessment for clinical relevance by the investigator. For adolescent subjects, the Central CRO will use age-and gender-specific reference values.

2.8.5.2 Vital signs

Analysis of the vital sign measurements using summary statistics for the change from baseline for each post-baseline visit will be performed. These descriptive summaries will be presented by vital sign and treatment group and separately in adults and adolescents. Change from baseline will only be summarized for subjects with both baseline and post-baseline values. Subjects with notable vital signs will be listed by study periods defined in Section 2.1.1.2. Newly occurring or worsening vital sign values outside of notable ranges will be summarized as needed. A case is considered as a newly occurring abnormality if the value is not notable or missing at baseline but is notable thereafter during the study. A case is considered as a worsening abnormality if the value is notable at baseline and at least one post-baseline value during the study is worse than baseline.

Notable values for adults and adolescents are defined as follows:

[figure not shown]
[figure not shown]
- heart rate of < 60 and > 100 bpm
- systolic blood pressure of < 90 and ≥ 140 mmHg
- diastolic blood pressure of < 60 and ≥ 90 mmHg

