16.1 Appendix 1: Clinically notable laboratory values and vital signs

Refer to [Appendix 1.1](#) for clinically notable vital sign values for adolescents.

Refer to [Appendix 2](#) for clinically notable laboratory values for hepatotoxicity.

Refer to [Appendix 3](#) for clinically notable laboratory values for nephrotoxicity.

The following other specific criteria have been identified for this study:

Platelets < 75 000/ μ L

- Any patient who have platelets < 75 000/ μ L after being randomized should discontinue study treatment.

For all other laboratory assessments, the Central Laboratory will flag laboratory values falling outside of the normal ranges on the Central Laboratory Report (which the investigator should review and sign-off) and the investigator will report any values considered clinically significant in the CRF as an AE.

Notable values for vital signs and change from baseline will be summarized.

Notable values for adults are defined as follows:

- heart rate of < 60 and > 100 bpm
- systolic blood pressure of < 90 and \geq 140 mmHg
- diastolic blood pressure of < 60 and \geq 90 mmHg

For ECGs a notable QTc value is defined as a QTcF interval of greater than 450 ms for males or greater than 460 ms for females – all such ECGs will be flagged by the Central CRO’s cardiologist and require assessment for clinical relevance by the investigator. For adolescent subjects, the Central CRO will use age-and gender-specific reference values.

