16.1.1 Appendix 1.1: Clinically notable vital signs – adolescent subjects

16.1.1.1 Guideline for pediatric blood pressure measurements:

Table 16-1 Best Blood Pressure (BP) Measurement Practices - Pediatrics

 1. The child should be seated in a quiet room for 3–5 min before measurement, with the back supported and feet uncrossed on the floor. 2. BP should be measured in the right arm for consistency, for comparison with standard tables, and to avoid a falsely low reading from the left arm in the case of coarctation of the aorta. The arm should be at heart level, supported, and uncovered above the cuff. The patient and observer should not speak while the measurement is being taken. 3. The correct cuff size should be used. The bladder length should be 80%–100% of the circumference of the arm, and the width should be at least 40%. 4. For an auscultatory BP, the bell of the stethoscope should be placed over the brachial artery in the antecubital fossa, and the lower end of the cuff should be 2–3 cm above the antecubital fossa. The cuff should be inflated to 20–30 mm Hg above the point at which the radial pulse disappears. Overinflation should be avoided. The cuff should be deflated at a rate of 2–3 mm Hg per second. The first (phase I Korotkoff) and last (phase V Korotkoff) audible sounds should be taken as systolic blood pressure and diastolic blood pressure. If the Korotkoff sounds are heard to 0 mm Hg, the point at which the sound is muffled (phase IV Korotkoff) should be taken as the diastolic BP, or the measurement repeated with less pressure applied over the brachial artery. The measurement should be read to the nearest 2 mm Hg. 5. To measure BP in the legs, the patient should be in the prone position, if possible. An appropriately sized cuff should be placed midhigh and the stethoscope placed over the popliteal artery. The systolic BP in the legs is usually 10%–20% higher than the brachial artery pressure. 
Adapted from Pickering TG et al 2005

--

Table 16-2 Upper and lower limits for adolescents’ vital signs that may be considered of concern if newly identified may be identified using the following table for guidance¹

Age	Systolic BP ^{2,3}	Diastolic BP ^{2,3}	HR ³
12 yrs	101-135	59-91	60-110
13 yrs	104-137	60-91	60-110

Age	Systolic BP ^{2,3}	Diastolic BP ^{2,3}	HR ³
14 yrs	106-140	60-92	60-110
15 yrs	107-142	61-93	60-110
16 yrs	108-145	63-94	60-110
17 yrs	108-147	64-97	60-100
18 yrs	-	-	60-100

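### SAP 2.8.5.2 applies the protocol's adult notable vital-sign limits to adolescents, so adolescent flags differ from those of Protocol Appendix 1 at every age from 12 to 17

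*SAP*

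**What the plan says.** Protocol Section 16.1 (Appendix 1) opens by pointing to Appendix 1.1 "for clinically notable vital sign values for adolescents". Further down it lists three limits under the line "Notable values for adults are defined as follows": heart rate below 60 or above 100 bpm, systolic pressure below 90 or at least 140 mmHg, and diastolic pressure below 60 or at least 90 mmHg.

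Appendix 1.1 contains Table 16-2, with a row for each year of age. Its title describes limits for adolescents' "vital signs that may be considered of concern if newly identified". The first row reads "12 yrs 101-135 59-91 60-110" (systolic, diastolic, heart rate).

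Protocol Section 12.5.2 says that subjects with notable vital signs, as Appendix 1 defines them, will be listed.

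SAP Section 2.8.5.2 states: "Notable values for adults and adolescents are defined as follows". It then gives "heart rate of < 60 and > 100 bpm", "systolic blood pressure of < 90 and ≥ 140 mmHg" and "diastolic blood pressure of < 60 and ≥ 90 mmHg", which are the protocol's adult numbers. The same section bases newly occurring and worsening abnormalities on whether the baseline value was notable.

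SAP Section 2.14.5 uses the same cut-offs, without an age split, for the hypertension, hypotension, bradycardia and tachycardia summaries in the final analysis. SAP Section 4, on changes to protocol-specified analyses, reads as not applicable.

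**The concern.** The protocol defines notable vital signs separately for adults and adolescents and makes that definition the basis of the listing. The SAP merges the two under the adult numbers without saying so. A programmer following the SAP would produce adolescent flags that are not the protocol's. A reader of the report, told that nothing changed, would take them for the protocol's flags.

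The merger looks unintended, because the SAP keeps age in view elsewhere. Section 2.8.4 takes laboratory ranges and notable criteria by age at the visit, Section 2.8.5.1 leaves adolescent ECGs to age- and gender-specific reference values, and Section 2.8.5.2 itself summarises change from baseline separately for adults and adolescents.

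What is at stake is the adolescent part of the vital-sign safety output. Protocol Section 4.1 names longer-term adolescent safety as one of the things this study is meant to support.

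**Working it through.** There is no stated figure to reproduce. The check compares two classification rules.

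**Inputs**
- SAP rule, all ages (Section 2.8.5.2): notable if systolic (SBP) < 90 or ≥ 140, diastolic (DBP) < 60 or ≥ 90, heart rate (HR) < 60 or > 100.
- Protocol rule, ages 12 to 17 (Table 16-2): notable if outside the range for that age, end points counted as inside.

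**Method.** For each age and each whole-number value, apply both rules and list the values on which they differ.

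| Age | Table 16-2 (SBP; DBP; HR) | Inside Table 16-2 but flagged by SAP | Outside Table 16-2 but not flagged by SAP |
|---|---|---|---|
| 12 | 101-135; 59-91; 60-110 | DBP 59, DBP 90-91, HR 101-110 | SBP 90-100, SBP 136-139 |
| 13 | 104-137; 60-91; 60-110 | DBP 90-91, HR 101-110 | SBP 90-103, SBP 138-139 |
| 14 | 106-140; 60-92; 60-110 | SBP 140, DBP 90-92, HR 101-110 | SBP 90-105 |
| 15 | 107-142; 61-93; 60-110 | SBP 140-142, DBP 90-93, HR 101-110 | SBP 90-106, DBP 60 |
| 16 | 108-145; 63-94; 60-110 | SBP 140-145, DBP 90-94, HR 101-110 | SBP 90-107, DBP 60-62 |
| 17 | 108-147; 64-97; 60-100 | SBP 140-147, DBP 90-97 | SBP 90-107, DBP 60-63 |

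**Reading the table**
- Every row has entries in both columns, so the rules disagree in both directions at every age.
- Heart rate is only ever over-flagged, and at 17 its limits coincide.
- High diastolic pressure never goes unflagged.
- Low systolic pressure goes unflagged at every age. The band is narrowest at 12 (90-100, 11 values) and widest at 16-17 (90-107, 18 values).
- High systolic pressure goes unflagged only at 12 and 13, and low diastolic pressure only at 15 to 17.

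Protocol Table 8-10 uses the mean of three blood pressure readings, so fractional values can occur. They shift the edges of the bands slightly but not the pattern.

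**The case against.** The strongest objection concerns the status of Table 16-2. Its title and first footnote present it as guidance for investigators screening for values of concern, to be weighed against the patient's disease, time course and condition. The second footnote bases the blood pressure columns on the 50th to 99th percentiles by height. If the lower bound is a 50th percentile, a systolic value just under it is merely below the median. About half of the reference population would then lie below that bound, and using it to define the hypotension category in SAP Section 2.14.5 would give an odd result. This stands: Table 16-2 cannot simply be dropped into Section 2.14.5. It does not rescue Section 2.8.5.2. Table 16-2 is the only adolescent definition in the protocol, Appendix 1 points to it, and Section 12.5.2 relies on Appendix 1 for the listing.

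Second, the reach is small. The Section 2.14.5 summaries cover only two subpopulations treated in the second half of a study that was terminated early. Section 2.8.5.2 produces a listing, with summaries of new or worsening values only as needed. Change-from-baseline summaries do not use the limits, and no efficacy result is touched. All of this stands and bounds the size of the point.

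Third, two figures are missing from the available text between the SAP's lead-in sentence and its bullets, so an adolescent table there cannot be wholly excluded. It is unlikely: the sentence assigns the limits to both groups, and Section 2.14.5 repeats the cut-offs without an age split.

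Fourth, SAP Amendment 2 removed the adolescent subgroup analysis. But adolescents remain in the safety set, and Section 2.8.5.2 still flags them.

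**Conclusion.** The inconsistency is real and undeclared. As written, the SAP yields adolescent notable flags that differ from the protocol's, in both directions, at every age from 12 to 17. The conclusion rests on Appendix 1.1 being the adolescent part of the Appendix 1 definition, and on no adolescent limits being hidden in the missing figures. The consequence is confined to descriptive safety outputs.

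Three stronger readings are not supported.
- A reader might infer that low blood pressure is missed mainly in younger adolescents. The unflagged systolic band in fact widens with age, and unflagged low diastolic values occur only at 15 to 17. Only the high systolic values at 12 and 13 are specific to younger subjects.
- A reader might work out a headcount from Protocol Section 5: 49 adolescents in CQGE031C2202 plus about 5% of the other planned subjects gives 0.05 × (2267 − 49) + 49 ≈ 160. That describes the preceding studies with everyone rolling over and being treated. It also counts CQGE031C1301, which has no adolescents, in the 5% base. The number of adolescents treated here is not stated.
- A reader might infer that an unflagged value is a missed clinical abnormality. Table 16-2 is guidance and does not support that.

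This point takes no position on which limits are clinically right. It says that the two documents must agree.

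**What to change.** In SAP Section 2.8.5.2, restrict the stated limits to subjects aged 18 or over at the visit. For adolescents, define the notable listing by reference to Protocol Appendix 1.1, Table 16-2, by age at the visit. The age basis must be written out: SAP Section 2.1 classifies by age at enrolment unless specified otherwise, whereas Section 2.8.4 already uses age at the visit for laboratory criteria. A note that Table 16-2 is guidance should accompany the listing.

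For the four categories in SAP Section 2.14.5, reconcile the cut-offs with Appendix 1, for example by labelling them as adult limits and reporting adolescents separately. If common limits are intended for either section, declare and justify them in SAP Section 4 instead.

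The listing change costs a sentence or two in the SAP and an age lookup in the program, with no new data. The Section 2.14.5 change also needs a decision on how adolescents are to be presented, so it is not purely a programming matter.
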